#### **Risks associated with repetitive TMS (FDA-designated minimal risk):**

Repetitive TMS has been considered “non-significant risk” by the FDA (2007) when applied at similar intensities, durations, and frequencies to those being used in this protocol. Additionally medial prefrontal and dorsolateral prefrontal continuous theta burst stimulation in a manner identical to this protocol has been designated minimal risk by the MUSC Institutional Review Board for healthy adults as well as individuals with nicotine dependence.

1. **Potential risk of a seizure:** In designing this experiment, we have followed the latest safety guidelines for TMS. Despite these precautions, there is a chance of a seizure as a result of rTMS. Eight seizures have been noted in previous studies, with six of them occurring in healthy volunteers without any history of seizures, brain tumors or traumatic brain injuries. All of these seizures have occurred during rTMS with the participant in the treatment chair and a trained operator on hand. All seizures have stopped by themselves without any medication. No participants have had any problems after the seizures. WFUHS has a plan for dealing with fainting and seizures, and **every TMS researcher involved in providing TMS treatment for this protocol (Key Personnel) will have extensive TMS training from the PI on the study as well as a skills test associated with collecting an accurate motor threshold (which is one of the largest factors that promotes safety).** Additionally, if a participant has a seizure an emergency response team will be called. Most seizures, including those caused by rTMS, last less than 60 seconds and do not require any medication. Participants will be evaluated by a physician associated with the WFUHS Brain Stimulation Laboratory following recovery from the seizure. Any participant who has a seizure cannot continue with the study.

**A note about theta burst stimulation:** The relative risk of having a seizure is related to the strength of the TMS stimulation (% motor threshold) and the frequency (typically 1Hz-20Hz, or theta). There are

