#### **Risks associated with MRI and TMS (minimal risk):**

1. Although the TMS protocol that we are using has never been associated with causing a seizure, individuals that have a history of seizures, stroke, or other neurological impairment that might lower their seizure threshold will be excluded from the study. All study personnel will have received a formal education course in seizure detection, care, and treatment and a physician will be available to immediately assist in stabilizing the participants in the event of a seizure. Any participant who has a seizure cannot continue with the study.
2. We will exclude individuals with claustrophobia such that they are not exposed to this risk. Additionally participants will be given a pressure sensitive squeeze ball that they can use to indicate at any time that they would like to leave the scanner.
3. To protect against hearing loss concerns, participants will wear high fidelity earplugs throughout the scanning session.
4. Participants will be informed of potential risk of scalp discomfort and headache before they consent and will be told that they should feel free to take non-steroidal antiinflammatory agents after the TMS session if they have a headache. We will also exclude individuals with chronic migraines such that they are not exposed to this risk.
5. We will exclude pregnant females such that they are not exposed to this risk.
6. All participants that enroll in this study will complete a written MRI safety screen. We will also use a handheld metal detector to ensure the participant has no metal in or on their body before entering the MRI scanning room.

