**Protocol for participants expressing suicidal ideation:** All study team members performing the Becks Depression Inventory will have received online training from the Suicide Prevention Resource Center (<https://training.sprc.org>). Completion documentation will be saved on the laboratory drive. In the event that a participant expresses a desire to kill themselves (selects answer #2 or #3 on question #9 of the Becks Depression Inventory), the trained study team member will ask them about the level of detail of their thoughts. If the participant has a suicide plan to kill himself/herself, the study staff will recommend he/she speaks with the suicide hotline and initiate contact with the suicide prevention hotline (Durham Center Crisis Line at [name]) while the individual is in their presence. If the participant refuses to talk to the hotline and leaves, the study staff will call 911. The study staff member will also contact the PI via phone, email, or text as soon as possible to inform them of the situation.

Participants may withdraw from the study at any time or may be withdrawn from the study if the PIs feel it is in the best interest of the participant. All key personnel will undergo appropriate IRB training for dealing with human participants and will be trained by the PI at their site in all aspects of the study.

interventions. Personnel listed in this protocol (as well as any rotating medical students, graduate students, psychiatry residents or fellows that may be exposed to this investigation as part of their research training exposure) will be required to maintain their certification of HIPAA training and Protection of Human Participants in Research training on an annual basis. Any new personnel without experience in human clinical research will be encouraged to attend the WFU Core Clinical Research Training Course, which is offered live and online throughout the year. Through these measures we will ensure that all study staff will be trained and will maintain ongoing understanding of research ethics and the rights of the participant during the consenting process and throughout an individual's participation in the study.

In the event of a medical emergency, a research participant will be transported to the Emergency Department at WFUHS. If a psychiatric crisis occurs, the Department of Psychiatry at either hospital will be contacted to arrange for either an emergency outpatient appointment or an in house psychiatric consult.

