**Quality Assurance Plan:** Weekly meetings will be held between the PIs and research team to discuss any data-related problems as well as qualitative comments received during data collection. Initial data analyses will examine distributions of variable scores, and comparability of baseline characteristics across conditions, any necessary adjustments to analyses will be made. Confidentiality protections are outlined below.

Statistical review of the study will be conducted annually by a Wake Forest biostatistician (including enrollment, retention, assessment inventories). Data collected in previous studies by our research group have demonstrated that after extended use in the MRI scanner environment (likely more than 5000 pulses) the strength of the induced magnetic field from the Magstim biphasic coil begins to drop in a non-linear fashion. Consequently, the intensity of the induced magnetic field from the Magstim coil will be assessed by protocol-approved study personnel and logged weekly (alongside with protocol use, number of pulses, intensity of pulses). This cumulative record of coil performance will be monitored and, when the intensity of the induced field had degraded 10%, we will switch to a new, identical Magstim coil.

**Definition and Reporting of AEs/SAEs to the IRB:** An adverse event (AE) is defined as any untoward medical occurrence in a study subject who was administered rTMS but does not necessarily have a causal relationship with this treatment. Any unwanted change, physically, psychologically or behaviorally, that occurs in a study participant during the course of the trial is an adverse event. A Serious Adverse Event (SAE) is defined as an adverse event that has one of the following outcomes: death, life-threatening, inpatient hospitalization or prolongation of existing hospitalization, persistent or significant disability/incapacity, a congenital anomaly/birth defect.

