**Reporting of Unanticipated Problems, Adverse Events or Deviations:** Any unanticipated problems, serious, and/or unexpected AEs, deviations or protocol changes will be reported within 24-72 business hours, depending on severity, by the principal investigator or designated member of the research team to the Wake Forest IRB and ME/DSMB.

**Management of SAEs or Other Study Risks:** As described above, SAEs will be immediately reported, within 24 business hours, to the ME/DSBM and Wake Forest IRB. For each SAE recorded, the research staff will follow the SAE until resolution, stabilization, or until the participant is no longer in the study as stated in the protocol. If applicable, copies of medical records and injury reports will be retrieved and safely stored in the subjects file. De-identified copies of reports will be sent to the Wake Forest IRB and ME/DSBM.

**Reporting of ME/DSMB Reports to IRB:** Any ME/DSMB reports will be reported to the Wake Forest IRB.

**Report of Changes or Amendments to the Protocol:** Any changes to the proposal/protocol must be approved by the Wake Forest IRB.

**Trial Stopping Rules:** The protocol will immediately be paused following notification of a SAE. Per IRB policy, the IRB and ME/DSMB will be notified within 24 business hours following the SAE notification. Should the reported SAE be confirmed as directly related to the protocol, the trial will be terminated. The device manufacturer will be notified within 72 business hours. Of note, according to the literature associated with the MagVenture device, there have been no clinical trials stopped or SAEs reported.

**Conflict of Interest:** Neither the PI, nor members of the research team have any Conflicts of Interest directly related to this protocol. The rTMS device used for the proposed study is manufactured by MagVenture.

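### The only trial-level pause is tied to an SAE, and the SAE definition does not capture a brief seizure without admission, so such a seizure does not by rule pause stimulation of other participants

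*Combined protocol and SAP*

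**What the plan says.** All references are to the combined protocol and SAP.

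- **Pause.** Trial Stopping Rules: "The protocol will immediately be paused following notification of a SAE". The same paragraph requires notice to the IRB and ME/DSMB within 24 business hours of the SAE notification. It ends the trial if the SAE is confirmed as directly related to the protocol.
- **SAE definition.** Definition and Reporting of AEs/SAEs to the IRB limits SAEs to adverse events with one of these outcomes: "death, life-threatening, inpatient hospitalization or prolongation of existing hospitalization, persistent or significant disability/incapacity, a congenital anomaly/birth defect". The underlying adverse event is one that "does not necessarily have a causal relationship with this treatment".
- **Seizure as described.** Risks associated with repetitive TMS lists seizure first and says: "Most seizures, including those caused by rTMS, last less than 60 seconds and do not require any medication". An emergency response team is called, and "Participants will be evaluated by a physician associated with the WFUHS Brain Stimulation Laboratory following recovery from the seizure". The medical-emergency paragraph under Protection Against Risks adds: "In the event of a medical emergency, a research participant will be transported to the Emergency Department at WFUHS".
- **Consequence of a seizure.** "Any participant who has a seizure cannot continue with the study". Risks associated with MRI and TMS repeats this.
- **Other reporting.** Unexpected AEs go to the IRB within 48 business hours. Unanticipated problems and serious or unexpected AEs go to the IRB and ME/DSMB within 24 to 72 business hours, according to severity. All AEs are also to be reported as the IRB requires. The closing section on unanticipated problems promises prompt reporting to the IRB.

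**The concern.** Seizure is the TMS hazard that the protocol puts first and the one its exclusions and operator training mainly address. A trial-level pause exists so that dose and screening can be checked before anyone else is stimulated. Here the pause depends on a definition built around outcome and admission, and the typical seizure the protocol describes can fall outside it.

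The result is an inversion. An AE need not be caused by rTMS, so an admission for an unrelated reason pauses the trial for everyone. A seizure in the treatment chair that resolves without admission does not. If staff follow the text exactly, other participants could continue to be stimulated before the ME/DSMB has considered whether intensity, motor-threshold measurement or screening played a part.

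**Working it through.** This is a check of rules against one case, with a short calculation on reporting times.

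**Case.** A participant has a seizure during a TMS visit. It lasts under 60 seconds, stops without medication, and the person is evaluated and not admitted.

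**Step 1: is it an SAE?**

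| Outcome in the definition | Met? |
|---|---|
| Death | No |
| Life-threatening | Only if someone judges it so |
| Inpatient hospitalization or its prolongation | No; an emergency team call, physician evaluation or Emergency Department transport is not admission |
| Persistent or significant disability | No |
| Congenital anomaly | No |

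Without a life-threatening judgement, 0 of 5 outcomes are met. There is no important-medical-event criterion to catch the case.

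**Step 2: does any other text pause the trial?**

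- Both risk sections withdraw the affected person only.
- Staff assess, for each AE, whether the intervention should be changed or discontinued. This allows a pause but does not require one.
- The principal investigator asks about safety at weekly team meetings. No pause is stated.
- The paragraph headed Management of SAEs or Other Study Risks deals only with SAEs.
- The reporting paragraphs, including the closing section on unanticipated problems, concern notice and state no pause.

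**Step 3: how much later could notice be?** An SAE goes to both bodies within 24 business hours. For a non-serious seizure judged unexpected:

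- IRB: the earlier of 48 and (24 to 72) gives 24 to 48 business hours. Less 24, that is 0 to 24 business hours later than for an SAE.
- ME/DSMB: (24 to 72) − 24 = 0 to 48 business hours later.

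**Step 4: would it be judged unexpected?** Probably, since Risks associated with MRI and TMS opens with "Although the TMS protocol that we are using has never been associated with causing a seizure". It is arguable, because seizure is also a listed risk. If it is judged expected, the protocol itself states no deadline. IRB requirements, which are not in the documents, may set one.

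**The case against.** **Discretion is provided for.** The AE assessment covers change or discontinuation of the intervention and is not worded as limited to the affected person. Life-threatening is a matter of judgement, and the investigator can stop dosing at any time. This stands: nothing forbids a pause. The gap is between an automatic pause and a judged one. But the protocol chose an automatic pause for every SAE, related or not, and it is hard to defend leaving the device's own leading hazard to judgement.

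**Reporting is largely covered.** This stands in full. A reader might infer that such a seizure could go unreported, or would reach the ME/DSMB only at its annual meeting. The documents do not support that. The 24-to-72-hour route reaches both bodies, an event that calls out an emergency team is a natural candidate for the 24-hour end, and the delay ranges above start at zero. Reporting under IRB requirements applies to all AEs, so it cannot be said that no deadline exists even for an expected seizure.

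**The harm is conditional.** It needs a seizure, no admission, no life-threatening judgement, no voluntary pause and continued dosing. A reader might infer that participants face a high seizure risk. The documents do not show that either. They note the lack of published safety tables for theta burst but cite at least 6 reviews pointing to low risk. They mention eight past seizures without a denominator. Enrolment is 48, at one institution. This limits the size of the point but does not close the gap in the rule.

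**A remedy brings its own difficulties.** An unlimited clause on seizures after TMS would run through follow-up to week 15 and could halt the trial for unrelated events, so a time limit is needed. A related seizure with admission would still end the trial, while the same seizure without admission would lead to review and possible restart. That discontinuity already exists in the present text and would remain.

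**Conclusion.** The gap in the pause rule is real. A self-limiting seizure without admission, and not judged life-threatening, meets none of the five SAE outcomes, and no other provision pauses TMS for other participants. The gap is at trial level only: exclusions, operator training, physician availability and withdrawal of the affected person still protect individuals.

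The reporting shortfall is secondary: at most 24 business hours later to the IRB and 48 to the ME/DSMB, possibly nothing, if the event is judged unexpected.

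This rests on reading inpatient hospitalization as excluding an Emergency Department visit, and on no life-threatening judgement being made. No probability of seizure or of harm is claimed. This is a foreseeable event that the stopping rule omits, and it is cheap to correct.

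**What to change.** In Definition and Reporting of AEs/SAEs to the IRB, name as an event of special interest:

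- any seizure during a TMS visit, or within a stated short window after stimulation (for example 24 hours); and
- any later seizure judged possibly related to TMS.

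In Trial Stopping Rules, state that such an event, whether or not the person is admitted:

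- pauses TMS for all participants;
- is notified to the IRB and ME/DSMB within 24 business hours; and
- is followed by an ad hoc ME/DSMB review of dose and screening, by email or call, before restart.

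Leave the termination rule for related SAEs unchanged. A general important-medical-event criterion would also close the gap, but it would make the seizure an SAE and so end the trial if it were confirmed as related. The narrower clause avoids that.

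**Cost.** A short amendment to two paragraphs, using the existing ME/DSMB and needing no new staff, procedures or data. The downside is a pause in TMS visits and an occasional ME/DSMB contact outside its annual meeting. The protocol gives no turnaround for such a contact, so the amendment should state one to keep the pause short.

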**Reporting of Unanticipated Problems, Adverse Events or Deviations**

Any unanticipated problems, serious and unexpected adverse events, deviations or protocol changes will be promptly reported by the principal investigator or designated member of the research team to the IRB.

